STUDY PROTOCOL

Nasal Intubation Using King Vision Video Laryngoscopy

[name]

(NCT03126344)

April 27, 2017

STUDY PROTOCOL

Title: A randomized controlled comparison of non-channeled King Vision, McGrath MAC video laryngoscope and Macintosh direct laryngoscope for nasotracheal intubation in patients with predicted difficult intubations.

Background: King Vision and McGrath MAC video laryngoscopes (VLs) are increasingly used. However, it remains unclear whether non-channeled King Vision or McGrath MAC VL, compared with conventional laryngoscope, provide shorter intubation time and a higher first success rate for NTI when used by experienced provider in management of predicted difficult intubation. It is also unclear whether non-channeled King Vision VL is superior to McGrath MAC VL when used for NTI.

Objective: To evaluate the performance of nasotracheal intubation in patients with predicted difficult intubations using non-channeled King Vision VL, McGrath MAC VL or Macintosh laryngoscope by experienced intubators.

Study Design: A single blind, three parallel arms, randomized controlled trial comparing NTIs using non-channeled King Vision VL, McGrath MAC VL and Macintosh DL in adults with predictors of difficult airways.

Subjects: Consecutive patients, between 18 and 60 years old with American Society of Anesthesiologists (ASA) classification of I or II, and requiring NTI for elective oral and maxillofacial surgery, were screened in the Preoperative Evaluation Unit of our institute.

Sample size: Based on the analysis of power analysis software, we take the type I error α as 0.05, the expected effect is 0.8, and the ideal test efficacy level is 0.8, then the minimum sample size of each group is 26. In order to reduce the loss of follow-up error, add 20% on this basis, then each group needs about 30 cases.

Recruitment method: Inpatients

Inclusion criteria: EGRI score 1–7.

Exclusion criteria: EGRI score > 7, history of reflux or diagnosed oesophageal disease, severe obstructive sleep apnea (OSA) and morbid obesity (body mass index > 40 kg/m²)

Study Methods:

1. Determine the subjects: select the patients who need nasotracheal intubation for elective operation, and determine 90 subjects strictly according to the inclusion and exclusion criteria, 30 in each group.

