The anesthesiologist tried to intubate when the Train of Four (TOF) count reached zero and BIS value decreased to 50. NTI was performed in a standard manner. First, a preformed ETT was inserted into the nostril and advanced to the posterior nasopharyngeal wall. Second, a laryngoscope blade was introduced into the mouth to expose the glottis. If it's necessary, the BURP maneuver (backward, upward, right-sided pressure) on the thyroid cartilage was attempted to obtain good glottis visibility. And ultimately, the ETT was inserted into the trachea with the aid of Magill's forceps, head flexion, or cuff inflation if necessary.

4. Observation outcome:

(1) Primary outcome: the intubation time

(2) Secondary outcome measures included time to expose the glottis (laryngoscopy time) and the view of glottis opening valued by Cormack-Lehane grade. A Cormack-Lehane grade IV was defined as laryngoscopy failure. A blinded investigator also recorded the hemodynamic changes (MAP, HR) during the procedure of NTI. The maximum values of invasive MAP were recorded. After successful intubation, the subjective sensation of the intubator (ease of device insertion, quality of view on display and ease of tube advancement) was graded as excellent, good, fair and poor. Other intubation parameters included incidences of bleeding or dental injury, number of assist maneuvers (use of BURP maneuver, Magill's forceps, or cuff inflation). Twenty-four hours after the procedure, a nurse anesthetist blinded to group assignment recorded the severity of sore throat and hoarseness.

Statistical analysis

Our sample size estimation was based on previous studies (11,23), in which the standard

deviations (SD) of intubation time were estimated as 8 and 13.7 seconds. To detect a intergroup difference of 10 seconds in intubation time with α of 0.05 and β of 0.8, we estimated that 30 patients would be enough for each group. To compensate for patients dropping out during the study, additional patients (10%) were added. The final sample size of 33 patients was in each group.

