Mean (SD) or Median (IQR [range]) was used to describe the parametric data. The number (percentage) was used to describe nonparametric data. Statistical analyses were performed with Prism 5.0 for Windows (GraphPad Software, Inc., La Jolla, California, USA). Binary data for three groups were analyzed using chi-square test and each two groups were compared with chi-square segmentation method or Fisher's exact test as appropriate. One-way analysis of variance (ANOVA) with post-hoc Bonferroni's Multiple Comparison test was used to analyze parameter data for changes within groups. The Kruskal-Wallis ANOVA with post-hoc Dunn's test was used to analyze ordinal data. A p value less than 0.05 was considered as significant.

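### With exactly three arms, single-step Bonferroni on intubation time is valid but stricter than needed; a Shaffer step-down on Welch p-values is an optional, cheap gain in power

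*Combined protocol and SAP*

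**What the plan says.** The Study Design section describes three parallel arms, and the Observation outcome section makes intubation time the primary outcome. The Statistical analysis section names "One-way analysis of variance (ANOVA) with post-hoc Bonferroni" comparisons and adds: "A p value less than 0.05 was considered as significant". It names no step-down or gated rule.

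Two parts of this reading are inferred:
- The per-pair threshold of 0.0167 follows from Bonferroni with three pairs, but it is not written.
- The sentence describes the ANOVA as being for within-group changes. I apply it to intubation time between devices because no other method is given for comparing a continuous outcome.

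The sample-size paragraph of the same section plans "To detect a intergroup difference of 10 seconds in intubation time with α of 0.05 and β of 0.8", taking SDs from earlier studies: "deviations (SD) of intubation time were estimated as 8 and 13.7 seconds". It concludes: "we estimated that 30 patients would be enough for each group". Then "additional patients (10%) were added", which gives 33. The Sample size and Study Methods sections give 30 per arm, so both numbers are used below.

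The Background section asks more than one pairwise question. It asks whether either video device improves on the conventional laryngoscope, and it says: "It is also unclear whether non-channeled King Vision VL is superior to McGrath MAC VL when used for NTI".

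**The concern.** Bonferroni holds every pair at 0.0167 whatever the other pairs show. It ignores the fact that three pairwise equalities among three means cannot be true or false independently. A step-down rule uses that fact. Applied to the same three p-values, it keeps every Bonferroni rejection and sometimes adds one.

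What is at stake is power on the primary outcome. The sizing is for one comparison at 0.05, while the analysis tests each pair at 0.0167. Some of that gap can be recovered without more patients, mainly for conclusions that involve more than one pair.

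**Working it through.** **Inputs.** From the Statistical analysis section: difference 10 s, alpha 0.05, SD 8 or 13.7 s, 30 then 33 per arm. Assumptions: two-sided tests, the stated β of 0.8 read as power of 0.80, and normally distributed times. The plan states no pattern for the three means, so several are shown.

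**1. The plan's own figure.** n = 2(z₀.₉₇₅ + z₀.₈₀)²·SD²/δ²
- SD 13.7: 2 × (1.960 + 0.842)² × 13.7²/10² = 29.5, rounded up to 30. This reproduces the plan.
- SD 8: 2 × (1.960 + 0.842)² × 8²/10² = 10.05, rounded up to 11.
- Dropout: 30 × 1.1 = 33.

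The 30 per arm therefore rests on SD 13.7 s and a single comparison at 0.05.

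**2. Power for one 10 s pair at 0.0167 (SD 13.7).** SE = 13.7·√(2/n), critical z = 2.394.
- n = 30: SE = 3.537, 10/3.537 = 2.827, Φ(2.827 − 2.394) = 66.7%. The exact value with the pooled three-arm t test is 65.0%; with Welch it is about 64%.
- n = 33: SE = 3.373, 10/3.373 = 2.965, Φ(2.965 − 2.394) = 71.6%. Pooled t gives 70.1%; Welch gives about 69%.

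**3. Why the step-down rule is valid.** The rule: reject the smallest p-value if it is at most 0.0167; if so, test the other two pairs at 0.05; otherwise stop. Among three means the number of true pairwise nulls is 3, 1 or 0. It cannot be 2, because two equalities imply the third.
- Three true: any error needs the smallest p-value to be at most 0.0167, with probability at most 3 × 0.0167 = 0.05.
- One true: only that pair can be falsely rejected, and never with p above 0.05.
- None true: no false rejection is possible.

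The argument requires each pairwise test to hold its own level.

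**4. Unequal SDs.** Pooled tests may fail that requirement. As an illustration, take SDs 13.7/13.7/8 with the first two arms equal and the third far away.
- Pooled variance = (2 × 13.7² + 8²)/3 = 146.5, so the pooled SD is 12.10 and 12.10/13.7 = 0.883.
- A nominal 1.960 then acts as 1.960 × 0.883 = 1.731, a two-sided error of about 8.3%.
- At the Bonferroni threshold, 2.394 × 0.883 = 2.115, about 3.4%.

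Simulation gives the same: 8.3% for the pooled step-down rule and for pairs at 0.05 after a significant ANOVA, against 3.4% for Bonferroni. With Welch p-values in the step-down rule, family-wise error is about 5.0% here, and about 5.0% with SDs 8/8/13.7.

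**5. Gain in power.** Simulation, at least 100,000 trials per scenario, SD 13.7 in all arms, one device 10 s from two equal ones, Welch tests:

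| Quantity | Bonferroni | Step-down |
|---|---|---|
| One 10 s pair, 30 per arm | 64% | 72% |
| One 10 s pair, 33 per arm | 69% | 77% |
| Both video devices faster (Macintosh the odd one out), 30 per arm | 49% | 65% |

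**6. Other patterns, 30 per arm** (pooled tests, equal SDs; Welch gives nearly the same gains):
- Means 0/5/10 s, SD 13.7: the 10 s pair goes from 65% to 67%, and a 5 s adjacent pair from 16% to 26%.
- Means 0/10/20 s, SD 13.7: a 10 s adjacent pair goes from 65% to 80%.
- SD 8, one device 10 s from two equal ones: 99.1% to 99.7%.
- Ordinary Holm, SD 13.7, one device 10 s from two equal ones: only 68%.

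**The case against.** The strongest reply is that nothing is broken. Bonferroni is standard and controls family-wise error. A reader might infer from the power comparison that the plan's analysis is wrong, or that its strictness buys nothing. The documents support neither. The section contains no contradiction or invalid inference on this point. It cites two quite different SDs, does not assign them to arms, and gives no basis for assuming equal variances across three devices. If pooled tests are used and SDs differ, Bonferroni's margin does protect: 3.4% against 8.3% in the illustration. This part stands. It is answered by using Welch p-values, not by dropping the step-down rule.

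A related temptation is to use the ANOVA already in the plan as a gate, followed by pairs at 0.05. With equal SDs that is valid and slightly more powerful. It shares the pooled-variance weakness, however, and with SDs 8/8/13.7 and all means equal its family-wise error is about 5.7%.

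Two further objections also stand. The gain of about 8 points belongs to one scenario and should not be quoted as a general effect. Nor does the step-down rule restore the planned 80% in that scenario: 72% and 77% both fall short. Bonferroni would need about 40 per arm, since 2 × (2.394 + 0.842)² × 13.7²/10² = 39.3.

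**Conclusion.** The point holds as an optional efficiency gain. Bonferroni is valid for three pairs, but testing the remaining pairs at 0.0167 after a first rejection is not needed for 5% family-wise control, provided each pairwise test holds its level.

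The gain of about 8 points per pair, and about 16 points for showing both video devices faster, rests on normal times, SD 13.7 s, and one device 10 s from two equal ones. It was positive in every pattern tried. For a 10 s pair it ranged from under 1 point (SD 8 s) or about 2 points (means 0/5/10 s) to about 15 points (means 0/10/20 s). The point also rests on reading the ANOVA sentence as the between-device analysis of intubation time, which the section should confirm.

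**What to change.** First, state in the Statistical analysis section that the sentence governs comparison of intubation time between devices. Then replace the Bonferroni step for that outcome with text such as:

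> The three pairwise p-values for intubation time will be computed with Welch (unequal-variance) t tests. The smallest is declared significant if it is at most 0.0167. If it is, each of the other two pairs is tested at 0.05; otherwise testing stops. Bonferroni-adjusted confidence intervals are reported for all three pairs.

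Fix the rule before outcome data are seen. The protocol is written largely in the past tense, so this needs confirming. If outcome data have already been seen, keep Bonferroni as the primary rule and label the step-down result post hoc.

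The cost is one or two sentences, with no new patients or data. The downside is that decisions and intervals will not always agree: a pair may be declared significant while its Bonferroni interval includes zero, and the report should say so. The conflict between 30 and 33 per arm needs reconciling separately.

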2. Group: Patients were randomly assigned to King Vision group, McGrath group or Macintosh group via a computer-generated randomization table: King Vision video laryngoscope group (group K, n = 30), McGrath MAC video laryngoscope group (group M1, n = 30) and Macintosh laryngoscope group (group M2, n = 30).

3. Anesthetic methods: the anesthetic methods of three groups were the same. Patients were asked which nostril was clearer. If both sides were equal and the surgeon had no objection, the right nostril was chosen.

No premedication was administered. Lactated Ringer's solution infusion was started intravenously to deal with the fluid loss from the overnight fast after entering the operating theatre. A standard preparation was then performed, including heart rate (HR), lead II ECG, SpO₂ (pulse oximetry), and end expiratory carbon dioxide. A Bispectral (BIS) index sensor was attached to the patient's forehead in conjunction with the BIS Monitor. Cannulation of right radial artery was performed under local anesthesia for invasive blood pressure monitoring.

All patients were preoxygenated by a facemask in the position of neutral. Prior to anesthesia induction, the nasal mucosa was well prepared with 1% tetracaine hydrochloride jelly for 2 min and five drops of ephedrine hydrochloride nitrofurazone (containing approximately 2 mg ephedrine) in all patients. Baseline hemodynamic data were recorded by an investigator after a stabilization period of 10 min.

The nasotracheal tube used was reinforced endotracheal tube (ETT, Safety-Flex with Murphy Eye, oral/nasal, Athlone, Ireland; ID 6.5mm in female and ID 7.0mm in male patients) and was well lubricated with 1 % tetracaine hydrochloride jelly. Dosing of induction medications was given at the discretion of the attending anesthesiologists. Induction agents included midazolam (0.02 mg/kg), propofol (1.5~2 mg/kg) and fentanyl (2 µg/kg). Upon loss of consciousness and jaw relaxation, manual ventilation was tested. If manual ventilation was available, cisatracurium besilate (0.15 mg/kg) was administered and post induction values were recorded 3 min after induction. Unsuccessful manual ventilation led to study exclusion.

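### MAP and HR during intubation have a recorded pre-induction baseline, but the plan does not adjust for it and leaves unclear which hemodynamic value is compared between devices

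*Combined protocol and SAP*

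**What the plan says.** Under Study Methods, 3. Anesthetic methods, the preparation common to all arms includes invasive pressure monitoring ("Cannulation of right radial artery was performed under local anesthesia for invasive blood pressure monitoring"). Before the induction drugs are described, the same section says: "Baseline hemodynamic data were recorded by an investigator after a stabilization period of 10 min". A second reading follows the drugs but still precedes laryngoscopy: "post induction values were recorded 3 min after induction".

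Under 4. Observation outcome, item (2), the hemodynamic secondary outcome reads: "A blinded investigator also recorded the hemodynamic changes (MAP, HR) during the procedure of NTI. The maximum values of invasive MAP were recorded". A maximum is named for MAP; no summary value is named for HR.

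The Statistical analysis section assigns chi-square or Fisher tests to binary data and Kruskal-Wallis with Dunn's test to ordinal data. For continuous data it says only: "One-way analysis of variance (ANOVA) with post-hoc Bonferroni's Multiple Comparison test was used to analyze parameter data for changes within groups". No covariate, ANCOVA, regression or repeated-measures model appears anywhere. The software is also named: "Statistical analyses were performed with Prism 5.0 for Windows".

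**The concern.** The trial records a baseline likely to predict the later MAP or HR, and the stated analysis does not use it as a covariate. With about 30 patients per arm and three Bonferroni-adjusted pairs, unexplained between-patient variation limits what the MAP and HR comparison can show. Part of that variation could be removed with data already collected.

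The second half of the problem is that the ANOVA sentence ends by tying the test to changes within groups and names neither MAP nor HR. Three readings are open:

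1. The maximum during intubation is compared between arms, and the baseline is ignored.
2. The change from baseline is compared between arms. The baseline is subtracted, which fixes its coefficient at 1 instead of estimating it.
3. Values are compared over time inside each arm. No between-device comparison of MAP or HR is then specified.

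An analyst could choose among these after seeing the data, and the choice affects precision.

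**Working it through.** **The plan's own figure.** The plan states no figure for MAP or HR. Its sample size is for intubation time: SD 13.7 s, difference 10 s, two-sided alpha 0.05, power 0.80. n = 2 × (1.960 + 0.842)² × (13.7/10)² = 29.5, so 30 per arm, and 30 × 1.10 = 33. Both match the Statistical analysis section. Intubation time has no baseline value, so nothing below alters that calculation.

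**Inputs for MAP.** From the documents: three arms of 30 and Bonferroni pairwise tests, taken as alpha 0.05/3 = 0.0167 two-sided. Assumed, because the documents are silent: the SD of the maximum (s_m), the SD of the baseline (s_b) and their correlation r, taken as 0.3, 0.5 and 0.6.

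**Residual variance under each analysis.**
- Maximum: s_m²
- Change: s_b² + s_m² − 2·r·s_b·s_m
- ANCOVA: s_m²·(1 − r²)

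Change minus ANCOVA equals (s_b − r·s_m)², which is never negative. Maximum minus ANCOVA equals r²·s_m², also never negative. So ANCOVA is at least as precise as either at any SD ratio, apart from estimating one slope. With 3 × 30 patients that costs a variance factor of about 1 + 1/85 = 1.012, so ANCOVA beats the maximum once r exceeds about 0.11.

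**Against the maximum.** This comparison does not depend on s_b.

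| r | SD factor √(1 − r²) | Fall in residual SD | Equivalent n, 30/(1 − r²) |
|---|---|---|---|
| 0.3 | 0.954 | 5% | 33 |
| 0.5 | 0.866 | 13% | 40 |
| 0.6 | 0.800 | 20% | 47 |

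**Against change scores.** This comparison does depend on s_b.

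| r | Equal SDs: ANCOVA/change = √((1 + r)/2) | Gain | s_b = 10, s_m = 15: change SD | ANCOVA SD | Gain |
|---|---|---|---|---|---|
| 0.3 | 0.806 | 19% | √235 = 15.33 | 14.31 | 7% |
| 0.5 | 0.866 | 13% | √175 = 13.23 | 12.99 | 2% |
| 0.6 | 0.894 | 11% | √145 = 12.04 | 12.00 | 0.3% |

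Change scores are less precise than the maximum only when r < s_b/(2·s_m). That is 0.5 with equal SDs, but 10/30 = 0.33 with SDs of 10 and 15.

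**In mmHg, for illustration.** Assume s_b = s_m = 15. The SE of a pairwise difference is 15 × √(2/30) = 3.87. By noncentral t (87 df for ANOVA, 86 for ANCOVA), the difference detectable with 80% power at alpha 0.0167 is 12.7 for the maximum. For change it is 15.1, 12.7 or 11.4 at r = 0.3, 0.5 or 0.6. For ANCOVA it is 12.2, 11.0 or 10.2. At r = 0, ANCOVA gives 12.8.

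In 20,000 simulated trials, power for a true 10 mmHg difference was 56% for the maximum and 60%, 70% or 78% for ANCOVA. With no true difference, the ANCOVA error rate per pair stayed at 1.7%.

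**The case against.** The strongest reply is that this is a preference about an outcome for which the trial was not sized. Unadjusted ANOVA between randomized arms is valid, and the documents set no target difference for MAP or HR, so they offer no yardstick for calling 12.7 mmHg too coarse. That stands, and it is why the point is minor. A reader might infer that the stated ANOVA is wrong or biased; nothing in the documents supports that.

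The size is also assumed. SD and correlation are not given, and the baseline precedes induction while the maximum follows drugs and airway instrumentation, so equal SDs cannot be taken for granted. A reader might infer that change scores always lose to the maximum below a correlation of 0.5, or that ANCOVA always gains 11% or more over them. Both hold only with equal SDs. The direction of the gain survives; its size over change scores does not.

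That the ANOVA sentence covers MAP and HR is itself an inference. The literal within-arm reading fits poorly with intubation time, which is a single value with no other method assigned, so a between-arm test is probably meant. The text does not settle this for MAP and HR.

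A last tempting inference concerns dosing: "Dosing of induction medications was given at the discretion of the attending anesthesiologists". The documents neither say nor exclude that doses differed by device, and baseline adjustment would not repair it, because the baseline precedes dosing. In the equal-SD illustration at r = 0.5, a 3 mmHg dose-driven shift would give a false positive in about 6.6% of trials per pair with ANCOVA, against 5.2% without. The 3-minute value also precedes laryngoscopy and is a possible covariate; it was not evaluated here.

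**Conclusion.** The point holds as a minor matter of efficiency and specification on secondary outcomes. A recorded baseline is not used as a covariate under either between-arm reading, and under the literal reading no comparison of devices on MAP or HR is specified.

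The gain over the unadjusted maximum rests only on the assumed correlation: modest at 0.3, material at 0.5 to 0.6, and nil near 0. The gain over change scores also depends on the SD ratio and may be negligible. The validity of an unadjusted between-arm ANOVA, the primary outcome and the sample size are untouched.

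**What to change.** In the Statistical analysis section, state that maximum MAP and maximum HR during intubation will each be compared between the three devices by ANCOVA, with device as factor and the pre-induction value of the same variable as covariate, followed by Bonferroni-adjusted pairwise comparisons of adjusted means. Under 4. Observation outcome, name maximum HR as the HR summary, since only MAP has one now. Say explicitly that the covariate is the pre-induction value and not the 3-minute value, which is recorded after discretionary dosing.

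This serves all three readings: it supplies the between-device comparison and removes the choice between maximum and change. It needs no extra patients, measurements or visits. The costs are possible use of software other than Prism 5.0, the assumption of a linear baseline effect with a common slope across arms, and one degree of freedom.

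### The 30 per group assumes one unadjusted comparison, but pairs are tested with Bonferroni: power for a given pair is about 65%, not 80%, at SD 13.7 s, and the test sentence needs correcting to a between-group comparison

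*Combined protocol and SAP*

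**What the plan says.** Section 4, Observation outcome, names one primary variable: "Primary outcome: the intubation time". The first paragraph of Statistical analysis takes from earlier studies standard "deviations (SD) of intubation time were estimated as 8 and 13.7 seconds", without saying which was used. It sets the target as "To detect a intergroup difference of 10 seconds in intubation time", with α 0.05 and a β of 0.8, and concludes that "we estimated that 30 patients would be enough for each group". Ten per cent is added for dropout: "The final sample size of 33 patients was in each group".

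The second paragraph assigns the tests. Binary data go to chi-square or Fisher's exact test, and ordinal data to Kruskal-Wallis with Dunn's test. For continuous data the only entry is one-way ANOVA with post-hoc Bonferroni, where the "Multiple Comparison test was used to analyze parameter data for changes within groups".

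Study Design describes three parallel arms. Background asks how each video laryngoscope compares with the conventional one, and whether King Vision is better than McGrath. That makes three pairs of devices.

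**The concern.** Two things do not fit together.

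First, the sizing and the test use different significance levels. The sample size treats the trial as one two-group comparison at 0.05. The analysis compares pairs with Bonferroni, so with three pairs each is tested at 0.05/3 = 0.0167. The stated 80% is then not the power of the pairwise test that answers the questions in Background. A reader who sees a non-significant pair would credit that result with more power than it had.

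Second, the sentence that carries the primary analysis refers to change inside a group. Intubation time has one value per patient, so it has no within-group change to test. The primary comparison should be readable from the plan without the reader having to assume a slip.

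**Working it through.** **Inputs.** Difference 10 s, SDs 8 s and 13.7 s, alpha 0.05, 30 and 33 per group: all from Statistical analysis. Three equal arms: Study Design. Assumptions made here: two-sided testing, β of 0.8 read as 80% power (the Sample size paragraph also gives 0.8 as the intended power), a common SD, and all three pairs tested.

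**The plan's own figure.** n per group = 2(z₁₋α/₂ + z₀.₈)² SD² / d².

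- SD 13.7 s, alpha 0.05: 2(1.960 + 0.842)² × 13.7² / 10² = 29.5, so 30. This matches the plan (an exact two-group t calculation gives 30.5).
- SD 8 s, alpha 0.05: 10.05, so 11.
- Root-mean-square of the two SDs (11.2 s), alpha 0.05: 20.
- SD 13.7 s, one-sided 0.05: 24.
- SD 13.7 s, alpha 0.05/3: 2(2.394 + 0.842)² × 13.7² / 10² = 39.3, so 40.

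Of these, only SD 13.7 s, two-sided and unadjusted, returns 30. Then 30 × 1.10 = 33.

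**Power of one pre-named pair under the stated test.** Noncentral t with the ANOVA pooled variance, df = 3(n − 1), noncentrality = d / (SD √(2/n)).

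- n = 30, SD 13.7 s: standard error 13.7 × √(2/30) = 3.54 s, noncentrality 10/3.54 = 2.83, df 87.
- n = 33, SD 13.7 s: standard error 13.7 × √(2/33) = 3.37 s, noncentrality 10/3.37 = 2.97, df 96.

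| SD | n per group | Power, alpha 0.05 | Power, alpha 0.05/3 |
|---|---|---|---|
| 13.7 s | 30 | 79.8% | 65.0% |
| 13.7 s | 33 | 83.5% | 70.1% |
| 8 s | 30 | – | 99.1% |
| 8 s | 33 | – | 99.5% |

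Simulation agrees with the two adjusted figures at SD 13.7 s (65% and 70%). The normal approximation gives 66.8% and 71.6%, and a two-group t-test 64.2% and 69.3%, so the method moves the answer by less than 2 points.

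**Equivalent statements at alpha 0.05/3 and SD 13.7 s.** The difference detectable with 80% power is 11.6 s at 30 per group and 11.1 s at 33. Reaching 80% for 10 s takes 41 evaluable per group (80.8%; 40 gives 79.7%).

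**Which n applies.** The 33 is 30 plus the dropout allowance. If that dropout occurs, about 30 per group are analysed and 65% is the relevant figure.

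**Overall F-test, SD 13.7 s, alpha 0.05.** Noncentrality = n Σ(μᵢ − μ̄)² / SD².

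- Means 0, 0, 10 s: Σ = 66.7. At n = 30, 30 × 66.7 / 187.69 = 10.66 and power is 83% (86% at 33).
- Means 0, 5, 10 s: Σ = 50. At n = 30, 30 × 50 / 187.69 = 7.99 and power is 70% (75% at 33).

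**The case against.** The strongest reply is that the plan names ANOVA first and Bonferroni only as post-hoc, and that the sizing sentence does not specify a pair. On that view the overall test matters. If one device stands 10 s apart from the other two, the F-test has 83% power at 30 per group, and at least one of the two truly different pairs reaches significance in about 80% of simulated trials. This stands, and it limits the point: the shortfall is for a given pair. It does not remove it, because Background asks about particular pairs and the F-test falls to 70% when the means are evenly spaced.

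A second reply is that everything depends on the SD. This also stands. At 8 s there is no shortfall, and 30 per group keeps 80% power per pair up to an SD of about 11.8 s. But 13.7 s is the quoted SD on which the plan's 30 rests.

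Three stronger readings are tempting, and the documents do not support them.

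- A reader might infer that the plan meant to test change within each arm, perhaps because the secondary outcomes include blood pressure and heart rate changes. One-way ANOVA with post-hoc comparisons, in a parallel-group trial sized on an intergroup difference, points to a slip for a between-group comparison.
- A reader might infer that the test for skewed times is left open, with inflated type I error. The plan sends all its continuous data to ANOVA and reserves Kruskal-Wallis for ordinal data. Only the descriptive summary, mean or median, is open, and nothing says that significance may be claimed from whichever test succeeds.
- A reader might infer that the trial must be enlarged. That does not follow either: the power shortfall is conditional on the SD, and stating it is enough.

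**Conclusion.** The point holds for the mismatch between sizing and test. At SD 13.7 s, a 10 s difference in any one pre-named pair would be found with about 65% power at 30 evaluable per group, or about 70% if none of the 33 is lost, against the 80% stated. The loss from Bonferroni is about 15 points at 30 (79.8% to 65.0%) and 13 at 33 (83.5% to 70.1%). These figures rest on two-sided testing, three pairs, a common SD and untransformed seconds. The within-groups wording is a drafting slip in the sentence that carries the primary analysis. It needs correcting, but it is not evidence that a wrong analysis was intended.

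**What to change.** Two wording changes in Statistical analysis.

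1. Replace the ANOVA sentence with: *Intubation time is compared between the three groups by one-way ANOVA with Bonferroni pairwise comparisons (alpha 0.0167 each).* The other continuous outcomes can be placed under the same between-group wording so that they keep a named test.

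2. Restate the power in the sample-size paragraph for that test, writing power where β now stands: *With Bonferroni adjustment over three pairs, each pairwise comparison has about 65% power for 10 s with 30 evaluable patients per group (70% if all 33 are analysed) at SD 13.7 s, and about 99% at SD 8 s.*

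The cost is a less favourable stated power. No new data, procedures or patients are needed. A sponsor who wanted 80% power per pair at SD 13.7 s would need 41 evaluable per group, but the fix does not depend on that.

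### Read literally, the plan tests repeated MAP and HR readings with a one-way ANOVA that has no patient term, which would mainly cause real haemodynamic changes to be missed

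*Combined protocol and SAP*

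**What the plan says.** Study Methods, item 3 (Anesthetic methods), sets two haemodynamic readings before intubation: "Baseline hemodynamic data were recorded by an investigator after a stabilization period of 10 min", and then "post induction values were recorded 3 min after induction". Item 4 (Observation outcome) adds readings around intubation among the secondary outcomes: "A blinded investigator also recorded the hemodynamic changes (MAP, HR) during the procedure of NTI". It also says: "The maximum values of invasive MAP were recorded". The number of time points during intubation is not given.

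The Statistical analysis section has one sentence that assigns a test to continuous data. It begins "One-way analysis of variance (ANOVA) with post-hoc", names Bonferroni's procedure, and ends "Multiple Comparison test was used to analyze parameter data for changes within groups". The significance threshold follows: "A p value less than 0.05 was considered as significant". The protocol nowhere mentions a paired test, a repeated-measures ANOVA, a mixed model or a patient effect.

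**The concern.** A change in MAP or HR within one device group is a comparison of each patient with himself or herself. An ordinary one-way ANOVA across time points has no term for the patient. It leaves the differences between patients in the error variance and takes the readings to be uncorrelated. Readings taken in one patient over a short period are likely to be positively correlated. With similar variances over time, the test then uses too large a standard error.

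What is at stake is the haemodynamic response to intubation under each device. If the test is underpowered for that response, a non-significant result could be taken as haemodynamic stability when a real change was present.

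**Working it through.** **The plan's own figure.** No power or precision is stated for the haemodynamic outcomes. The only sample-size figure that can be set beside this check is the 30 per group for intubation time. With a 10 s difference, the larger SD of 13.7 s, two-sided alpha 0.05 (sidedness assumed) and 80% power, n = 2 × (1.96 + 0.84)² × 13.7² / 10² = 29.4, rounded up to 30. This reproduces the figure. It matters here only as the number of patients per arm used below (the final planned number is 33).

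**Inputs.**
- From the protocol: 30 patients per arm (Study Methods, item 2); readings at baseline, 3 min after induction and during intubation; threshold 0.05.
- Assumed: three readings in all; equal variances; a common within-patient correlation ρ of 0.3, 0.5 or 0.7; a true change of 0.5 SD at one reading; Bonferroni over three pairs, so 0.05/3 = 1.67% per pair.

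**Standard error of a change.** Let σ² be the variance of one reading.
- True variance of the mean change: 2σ²(1 − ρ)/n.
- Variance used by ordinary one-way ANOVA: 2σ²/n.
- Ratio of standard errors, ANOVA to true: 1/√(1 − ρ).
- ρ = 0.3: 1/√0.7 = 1.20. ρ = 0.5: 1/√0.5 = 1.41. ρ = 0.7: 1/√0.3 = 1.83. The ratio is 1 only at ρ = 0.

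**Error rate and power for one pair, by simulation (100,000 datasets).**

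| ρ | Type I error, one-way ANOVA contrast (nominal 1.67%) | Power for 0.5 SD, one-way ANOVA contrast | Power for 0.5 SD, paired t at 1.67% |
|---|---|---|---|
| 0.3 | about 0.5% | 28% | 42% |
| 0.5 | about 0.1% | 25% | 58% |
| 0.7 | below 0.01% | 21% | 83% |

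**Overall F test, by a separate simulation (40,000 datasets).** The pattern is the same. At nominal 5%, the type I error of ordinary one-way ANOVA is 1.5%, 0.4% and 0.01% for the three correlations. Its power is 45%, 43% and 39%, against 64%, 79% and 96% for repeated-measures ANOVA.

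**Unequal variances.** One MAP quantity is a per-patient maximum, whose spread may differ from that at baseline. Take SDs of 1, 1 and 2 (assumed).
- Pooled variance: (1 + 1 + 4)/3 = 2, so the ANOVA variance of a difference is 2 × 2/n = 4/n.
- True variance, baseline against maximum: (1 + 4 − 2 × ρ × 1 × 2)/n = (5 − 4ρ)/n.
- ρ = 0.3: √(4/3.8) = 1.03. ρ = 0.1: √(4/4.6) = 0.93.

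The overstatement nearly vanishes in the first case, and in the second the standard error is slightly too small.

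**The case against.** The strongest reply is that the sentence does not name MAP or HR, and that its reference to change within groups may be loose English for a comparison among the three arms. It is the only sentence that assigns a test to continuous data, and the sentence before it concerns binary data in the three groups. Read literally, it would leave intubation time, the primary outcome, without a stated between-arm test. Applied across arms to one value or one change score per patient, one-way ANOVA does not breach independence. This stands as a real ambiguity, and so the point is conditional. It does not rescue the plan: on that reading no test of within-patient change is specified at all. It is also possible that a repeated-measures form of one-way ANOVA was intended, but the text does not say so.

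A reader might infer three stronger things that the documents do not support.
- *Every haemodynamic standard error is wrong in the same direction.* The unequal-variance example shows that the direction depends on quantities the protocol does not give.
- *Spurious pressor responses will be found.* With equal variances and positive correlation the test is conservative, so false positives become rarer.
- *Devices will be compared by noting which arms show a significant rise.* The plan nowhere says this. The device-by-time contrast is recommended because the plan names none for MAP or HR, not because it commits to the wrong inference.

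**Conclusion.** The point holds in conditional form. If the sentence means what it says and covers MAP and HR, the stated test ignores the pairing of readings within patients. Under the equal-variance assumptions above, the standard error of a change is overstated by 20% to 83%, and power for a 0.5 SD change falls by 14 percentage points at ρ = 0.3 (42 − 28), 33 at 0.5 (58 − 25) and 62 at 0.7 (83 − 21). These sizes rest on an assumed correlation, three readings and equal variances, none of which the protocol states. With unequal variances the error can be negligible or slightly reversed.

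The reach is limited to secondary haemodynamic outcomes. This error does not touch the analysis of intubation time, which has one value per patient, or the sample size. The correction is worth making because it is nearly free and the sentence needs rewriting on either reading.

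**What to change.** Replace the sentence, as it applies to MAP and HR, with the following.
1. List the time points at which MAP and HR are analysed, and say whether the maximum MAP is one of them or a separate outcome.
2. Name a repeated-measures analysis: either repeated-measures ANOVA with a sphericity correction, or a mixed model with a patient effect and terms for device, time and device-by-time. In the mixed model, choose a covariance structure that allows variances to differ between time points; a random intercept alone does not.
3. Use paired contrasts from that analysis for change within a device, and the device-by-time contrast for any comparison of devices.
4. State separately that one-way ANOVA across the three arms applies to continuous outcomes with one value per patient, such as intubation time and laryngoscopy time.

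The cost is a few lines of analysis text. The readings are already in the plan, so no extra patients or measurements are needed.
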